**6.6. Concomitant medications/products and concomitant vaccinations**

At each study visit/contact, the investigator or delegate should question the subject about any medications/products taken and vaccinations received by the subject.

**CONFIDENTIAL**207759 (NTHI MCAT-008)  
Protocol Amendment 3 Final**6.6.1. Recording of concomitant medications/products and concomitant vaccinations**

The following concomitant medication(s)/product(s)/vaccine(s) must be recorded in the eCRF.

- All concomitant vaccines or medications or products, associated with an AE, except vitamins and dietary supplements, administered during the entire study period following the first dose of study vaccine (Day 1 to Day 721).
- Prophylactic medication (i.e. medication administered in the absence of ANY symptom and in anticipation of a reaction to the vaccination).  
E.g. an anti-pyretic is considered to be prophylactic when it is given in the absence of fever and any other symptom, to prevent fever from occurring [fever is defined as temperature  $\geq 37.5^{\circ}\text{C}$ ]. The preferred location for measuring temperature in this study will be the oral cavity or the axilla.
- Any concomitant medications/products/vaccines listed in Section 6.6.2.
- Any concomitant medications/products/vaccines relevant to a SAE/pIMD to be reported as per protocol or administered at any time during the study period for the treatment of a SAE/pIMD. In addition, concomitant medications relevant to SAEs and pIMD need to be recorded on the expedited Adverse Event report.

**6.6.2. Concomitant medications/products/vaccines that may lead to the elimination of a subject from per-protocol analyses**

The use of the following concomitant medications/products/vaccines will not require withdrawal of the subject from the study but may determine a subject's evaluability in the per-protocol analysis. See Section 10.5 for cohorts to be analysed.

- Any investigational or non-registered product (drug or vaccine) other than the study vaccines used during the study period.
- Immunosuppressants or other immune-modifying drugs administered chronically (i.e. more than 14 days in total) during the study period. For corticosteroids, this will mean prednisone  $\geq 20$  mg/day, or equivalent. Inhaled and topical steroids are allowed.
- Long-acting immune-modifying drugs administered at any time during the study period (e.g. infliximab).
- A vaccine not foreseen by the study protocol administered during the period starting 30 days before the first dose and ending at 30 days after the last dose of vaccine administration\*, with the exception of any influenza or pneumococcal vaccine which may be administered  $\geq 15$  days preceding or following any study vaccine dose.

**CONFIDENTIAL**207759 (NTHI MCAT-008)  
Protocol Amendment 3 Final

\* In case an emergency mass vaccination for an unforeseen public health threat (e.g.: a pandemic) is organised by the public health authorities, outside the routine immunisation program, the time period described above can be reduced if necessary for that vaccine provided it is licensed and used according to its Summary of Product Characteristics (SmPC) or Prescribing Information and according to the local governmental recommendations and provided a written approval of the Sponsor is obtained.

- Immunoglobulins and/or any blood products administered during the study period.
- Drug and/or alcohol abuse.

### **6.7. Intercurrent medical conditions that may lead to elimination of a subject from per-protocol analyses**

At each study visit subsequent to the first vaccination, it must be verified if the subject has experienced or is experiencing any intercurrent medical condition that may lead to elimination from per-protocol analyses. If it is the case, the condition(s) must be recorded in the eCRF.

Subjects may be eliminated from the per-protocol cohort for immunogenicity if, during the study, they incur a condition that has the capability of altering their immune response or are confirmed to have an alteration of their initial immune status.

## **7. HEALTH ECONOMICS**

Not applicable.

## **8. SAFETY**

The investigator or site staff is/are responsible for the detection, documentation and reporting of events meeting the criteria and definition of an adverse event (AE) or serious adverse event (SAE) as provided in this protocol.

Each subject will be instructed to contact the investigator immediately should they manifest any signs or symptoms they perceive as serious.

### **8.1. Safety definitions**

#### **8.1.1. Definition of an adverse event**

An AE is any untoward medical occurrence in a clinical investigation subject, temporally associated with the use of a medicinal product, whether or not considered related to the medicinal product.

**CONFIDENTIAL**207759 (NTHI MCAT-008)  
Protocol Amendment 3 Final

An AE can therefore be any unfavourable and unintended sign (including an abnormal laboratory finding), symptom, or disease (new or exacerbated) temporally associated with the use of a medicinal product. For marketed medicinal products, this also includes failure to produce expected benefits (i.e. lack of efficacy), abuse or misuse.

Examples of an AE include:

- Exacerbation of a chronic or intermittent pre-existing condition including either an increase in frequency and/or intensity of the condition.
- New conditions detected or diagnosed after study vaccine administration even though they may have been present prior to the start of the study.
- Signs, symptoms, or the clinical sequelae of a suspected interaction.
- Signs, symptoms temporally associated with study vaccine administration.
- Pre- or post-treatment events that occur as a result of protocol-mandated procedures (i.e. invasive procedures, modification of subject's previous therapeutic regimen).

AEs to be recorded as endpoints (solicited AEs) are described in Section 8.1.3. All other AEs will be recorded as UNSOLICITED AEs.

Examples of an AE DO NOT include:

- Medical or surgical procedures (e.g. endoscopy, appendectomy); the condition that leads to the procedure is an AE/SAE.
- Situations where an untoward medical occurrence did not occur (e.g. social and/or convenience admission to a hospital, admission for routine examination).
- Anticipated day-to-day fluctuations of pre-existing disease(s) or condition(s) present or detected at the start of the study that do not worsen.
- Pre-existing conditions or signs and/or symptoms present in a subject prior to the first study vaccination. These events will be recorded in the medical history section of the eCRF.

### **8.1.2. Definition of a serious adverse event**

A SAE is any untoward medical occurrence that:

- a. Results in death,
- b. Is life-threatening,

Note: The term 'life-threatening' in the definition of 'serious' refers to an event in which the subject was at risk of death at the time of the event. It does not refer to an event, which hypothetically might have caused death, had it been more severe.

- c. Requires hospitalisation or prolongation of existing hospitalisation,

Note: In general, hospitalisation signifies that the subject has been admitted at the hospital or emergency ward for observation and/or treatment that would not have been appropriate in the physician's office or in an out-patient setting. Complications

**CONFIDENTIAL**207759 (NTHI MCAT-008)  
Protocol Amendment 3 Final

that occur during hospitalisation are also considered AEs. If a complication prolongs hospitalisation or fulfils any other serious criteria, the event will also be considered serious. When in doubt as to whether ‘hospitalisation’ occurred or was necessary, the AE should be considered serious.

Hospitalisation for elective treatment of a pre-existing condition (known or diagnosed prior to informed consent signature) that did not worsen from baseline is NOT considered an AE.

d. Results in disability/incapacity, OR

Note: The term disability means a substantial disruption of a person’s ability to conduct normal life functions. This definition is not intended to include experiences of relatively minor medical significance such as uncomplicated headache, nausea, vomiting, diarrhoea, influenza like illness, and accidental trauma (e.g. sprained ankle) which may interfere or prevent everyday life functions but do not constitute a substantial disruption.

e. Is a congenital anomaly/birth defect in the offspring of a study subject.

Medical or scientific judgement should be exercised in deciding whether reporting is appropriate in other situations, such as important medical events that may not be immediately life-threatening or result in death or hospitalisation but may jeopardise the subject or may require medical or surgical intervention to prevent one of the other outcomes listed in the above definition. These should also be considered serious. Examples of such events are invasive or malignant cancers, intensive treatment in an emergency room or at home for allergic bronchospasm, blood dyscrasias or convulsions that do not result in hospitalisation.

### 8.1.3. Solicited adverse events

Solicited local and general AEs occurring during a 7-day follow-up period after each vaccination (i.e. the day of vaccination and the 6 subsequent days) and unsolicited AEs occurring during a 30-day follow-up period after each vaccination (i.e. the day of vaccination and the 29 subsequent days), will be reported via diary cards. In addition, subjects will be asked at Phone contacts if there were any safety concerns in the last 7 days; this information will be recorded via the appropriate section of the eCRF.

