**Table 6 Intervals between study visits****(Amended 26 May 2020)**

| Interval                  | Optimal length of interval | Allowed interval  |
|---------------------------|----------------------------|---|
| Visit 1 → Phone contact 1 | 7 days                     | 7 - 9 days  |
| Visit 1 → Visit 2         | 30 days                    | 30 - 45 days  |
| Visit 1 → Visit 3         | 60 days                    | 60 - 75 days    |
| Visit 3 → Phone contact 2 | 7 days                     | 7 - 9 days  |
| Visit 3 → Visit 4         | 30 days                    | 30 - 45 days    |
| Visit 3 → Visit 5         | 120 days                   | 120 - 150 days    |
| Visit 5 → Phone contact 3 | 7 days                     | 7 - 9 days  |
| Visit 5 → Visit 6         | 30 days                    | 30 - 45 days    |
| Visit 5 → Visit 7         | 180 days                   | 180 - 210 days    |
| Visit 7 → Phone contact 4 | 7 days                     | 7 - 9 days  |
| Visit 7 → Visit 8         | 30 days                    | 30 - 45 days    |
| Visit 7 → Visit 9         | 180 days                   | 180 - 210 days    |
| Visit 7 → Visit 10        | 360 days                   | 360 - 390 days (+120 days under special circumstances) |

 Subjects will not be eligible for inclusion in the per-protocol set (PPS) for analysis of immunogenicity if the study visit is performed outside this interval.

 **Refer to Section 5.6.18 for study procedures to be considered during special circumstances. Impact on the per protocol set for immunogenicity will be determined on a case by case basis**

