### **4. ENDPOINTS**

#### **4.1. Primary endpoints**

##### **Safety**

Solicited local and general symptoms.

- Occurrence of each solicited local and general symptom (any and Grade 3) reported within 7 days (Day 1 – Day 7) after each vaccination, within each vaccination schedule.

**CONFIDENTIAL**207759 (NTHI MCAT-008)  
Statistical Analysis Plan Amendment 1 Final

Unsolicited adverse events.

- Occurrence of each unsolicited AE reported within 30 days (Day 1 – Day 30) after any vaccination, according to the Medical Dictionary for Regulatory Activities (MedDRA) classification, within each vaccination schedule.

Serious adverse events.

- Occurrence of any serious adverse events reported from Day 1 (Visit 1) up to and including Day 541 (Visit 9), within each vaccination schedule.

Potential immune-mediated diseases (pIMDs).

- Occurrence of pIMDs reported from Day 1 (Visit 1) up to and including Day 541 (Visit 9), within each vaccination schedule.

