**5.1.1. Exposed set**

The exposed set (ES) will include all subjects with at least 1 study vaccine administration documented, with respect to the vaccine actually administered:

- A safety analysis will be based on the Exposed, Solicited and Unsolicited Sets:
  - Solicited Set will include all subjects in the exposed set that provided solicited safety data;
  - Unsolicited Set will include all subjects in the exposed set that reported having/not having unsolicited AEs.

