**5.2.1.1. Elimination from Solicited Safety Set**

Code 1030, code 900 and code 1160 will be used to identify subjects eliminated from the Solicited Safety Set. Code 1070 will be used to identify subjects eliminated from the Solicited Safety Set by visit when vaccination is not administered at that visit.

**CONFIDENTIAL**207759 (NTHI MCAT-008)  
Statistical Analysis Plan Amendment 1 Final**5.2.1.2. Elimination from Unsolicited Safety Set**

Code 1030, code 900 and code 1150 will be used to identify subjects eliminated from the Unsolicited Safety Set.

Code 1150 will be attributed to subjects if all the following conditions are met:

- did not complete the safety assessment following the 7-day follow-up period after each vaccination (i.e. phone contacts),
- did not return any paper Diary after each vaccination,
- did not return for the scheduled visit 30-days after each vaccination,
- did not report any unsolicited AE.

Code 1070 will be used to identify subjects eliminated from the Solicited Safety Set by visit when vaccination is not administered at that visit.

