- the duration of solicited adverse events will be calculated as the sum of the consecutive days with the symptom reported at Grade 1 or higher. The duration of solicited events at a specific grade (e.g., Grade 3) will be calculated as the sum of the consecutive days with the symptom reported at that grade. The same rule applies for solicited adverse events ongoing at the end of the solicited follow-up period considering the maximum intensity reported;
- when the occurrences of solicited adverse events are summarised, each event recorded as having occurred during a specific period will be counted as the number of occurrences the event is consecutively reported (at Grade 1 or higher);
- when the occurrences of solicited adverse events at a specific grade are summarised, each event recorded as having occurred at that grade during a specific period will be counted as the number of occurrences the event is consecutively reported at that grade.

For analysis of unsolicited adverse events, such as serious adverse events or adverse events by primary MedDRA term, and for the analysis of concomitant medications, all vaccinated subjects will be considered. Subjects who did not report the event or the concomitant medication will be considered as subjects without the event or the concomitant medication respectively. Note that for all tables described in this section, the way the percentage of subjects will be derived will depend on the event analysed (see table below for details). As a result, the N value will differ from one table to another.

**CONFIDENTIAL**207759 (NTHI MCAT-008)  
Statistical Analysis Plan Amendment 1 Final

Event	N used for deriving % per subject for Vaccination phase	N used for deriving % per dose for Vaccination phase
Concomitant vaccination	All subjects with study vaccine administered	
Solicited local/general symptom	All subjects, with study vaccine administered, with at least one solicited symptom, either local or general, documented as either present or absent (i.e., symptom screen completed)	All study visits with study vaccine administered and with at least one solicited symptom, either local or general, documented as either present or absent (i.e., symptom screen completed)
Unsolicited symptom with onset within 30 days	All subjects, with study vaccine administered, that have safety data	
Unsolicited symptom (e.g., SAEs, AEs leading to withdrawal,..)	All subjects with study vaccine administered	

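### The 30-day unsolicited AE denominator keeps dosed subjects seen only at the phone call 7-9 days after a dose, or followed only after another dose, and counts them as event-free

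*Protocol*

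**What the plan says.** - **Endpoint.** SAP 4.1, like protocol 10.1, lists as primary "Occurrence of each unsolicited AE reported within 30 days (Day 1 – Day 30) after any vaccination". SAP 6.5.2.3 tabulates these events both after any and after each vaccination.
- **Source.** Protocol 8.1.3 collects unsolicited AEs over 30 days ("i.e. the day of vaccination and the 29 subsequent days), will be reported via diary cards"). Under protocol 5.6.17 the cards are collected at Visits 2, 4, 6 and 8.
- **Phone contact.** Protocol Table 6 (row "Visit 1 → Phone contact 1" and the matching rows for the later doses) allows the call 7-9 days after the dose. Protocol 8.1.3 adds that "subjects will be asked at Phone contacts if there were any safety concerns in the last 7 days".
- **Analysis set.** SAP 5.1.1 states the intention: "Unsolicited Set will include all subjects in the exposed set that reported having/not having unsolicited AEs". SAP 5.2.1.2 implements it with code 1150: "Code 1150 will be attributed to subjects if all the following conditions are met". The first of the four conditions is that the subject "did not complete the safety assessment following the 7-day follow-up period after each vaccination (i.e. phone contacts"). The other three are no diary returned, no return for the 30-day visit, and no unsolicited AE reported.
- **Denominator.** The N table in SAP 11.2.5 uses, for unsolicited symptoms with onset within 30 days, "All subjects, with study vaccine administered, that have safety data". The text above that table considers all vaccinated subjects and counts those who did not report an event as without it. Protocol 10.6 has the same non-reporter rule.
- **Which sets.** SAP 6.5.2.3 bases the unsolicited analyses on both the Exposed Set and the Unsolicited Safety Set.

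**The concern.** The four conditions of code 1150 must hold together, so a single contact is enough to keep a subject in. Two kinds of dosed subject then enter the 30-day denominator without 30-day information:

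- a subject reached by phone 7-9 days after the dose, with no diary, no 30-day visit and no later contact;
- a subject followed after one dose but not after another. Code 1150 is assigned per subject, and its phrase about each vaccination does not say whether doses are judged separately. The by-visit code mentioned in that section (1070) deals only with doses that were not given.

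Such a dose adds fully to the denominator but can add to the numerator only for the days actually observed. Rates of a primary safety endpoint, and their upper confidence limits, come out too low. The tables after each vaccination are the most exposed, including those for the third active dose, which is the study's focus.

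The SAP is stricter for solicited AEs: SAP 11.2.5 excludes doses without a documented symptom sheet. Unsolicited AEs have no such per-dose rule, although SAP Amendment 1 was written partly to define the safety sets.

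**Working it through.** **1. The rule applied to one case.** Take a subject who is dosed and completes the call, but has no diary, no 30-day visit, no later contact and no AE report.

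- Code 1150, condition 1 (no phone assessment): not met.
- Conditions 2-4 (no diary, no visit, no AE): met.
- All four are required, so the code is not assigned and the subject stays in the set.
- The subject has some safety data, so counts in N, and as a non-reporter counts as event-free for Day 1-30.
- A call 7-9 days after the dose falls on Day 8-10. Observed share of the window: 8/30 = 27% to 10/30 = 33%. Unobserved: 20-22 days.

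**2. The plan's own figure.** Protocol Table 19 gives, for 30% of 100 subjects, an exact 95% interval of 21.2-40.0. Clopper-Pearson for 30/100 reproduces 21.2-40.0.

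**3. Size of the bias.** The inputs are assumptions, because the documents give neither the AE rate nor the share affected:

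- true 30-day rate p = 30%;
- share f of dosed subjects followed only to day c, with f = 2%, 5%, 10% and c = 8 to 10;
- constant hazard over the 30 days, with events before the call captured.

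Reported rate = (1 − f)·p + f·[1 − (1 − p)^(c/30)].

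The bracket is 1 − 0.7^(8/30) = 0.091 for c = 8 and 1 − 0.7^(10/30) = 0.112 for c = 10.

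| f | Calculation (c = 8; c = 10) | Reported rate | Shortfall, points |
|---|---|---|---|
| 2% | 0.294 + 0.02 × 0.091; 0.294 + 0.02 × 0.112 | 29.6% | 0.4 |
| 5% | 0.285 + 0.05 × 0.091; 0.285 + 0.05 × 0.112 | about 29.0% | about 1.0 |
| 10% | 0.270 + 0.10 × 0.091; 0.270 + 0.10 × 0.112 | 27.9-28.1% | about 2.0 |

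**4. Effect on the interval at f = 10%, N = 100.** Reported 28/100 has an exact 95% interval of 19.5-37.9. Full follow-up, 30/100, has 21.2-40.0. The upper limit is 40.0 − 37.9 = 2.1 points too low.

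**5. Any versus each vaccination.** The calculation is for one dose. For the rate after any vaccination, a subject lost after one dose usually has follow-up after others, so the shortfall is smaller.

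**The case against.** The strongest reply is that the protocol has several safeguards and that the call is not the root cause.

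- **Other ascertainment.** The call is additional to the diary. Protocol 8.3.3.1 gives an open question reaching back to the vaccination or previous visit, and protocol 5.6.17 refers to a telephone script that is not in the documents. AEs are recorded at every later visit and contact (Table 5), unreturned diaries are sought (5.6.17), and subjects who miss visits get three calls and a certified letter (9.2.1). This stands: a missed 30-day visit does not by itself end follow-up, and the gap is limited to doses with no later information. It does not change the rule for those doses.
- **Not only the call.** Protocol 10.6 and the Exposed Set analysis in SAP 6.5.2.3 count non-reporters as event-free even with no contact at all. This also stands, and it means that changing code 1150 alone is not enough.
- **Descriptive analysis.** Protocol 10.10 plans no comparisons, and procedures are the same in both arms. That limits the consequence but does not remove a downward bias in the estimates themselves.

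A reader might infer three stronger points that the documents do not support:

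- *At a 10% share, 30% would be reported as 27%, with an upper limit 3.8 points too low.* This gives phone-only subjects no events, although the call can capture early ones. It also compares 27/100 (upper limit 36.8) with 27/90 (upper limit 40.6), so part of the 3.8 points is only the smaller sample.
- *A call 9 days after the dose leaves the first 2 days of the solicited window uncovered.* Solicited AEs come from daily diary cards, so the recall period of the call leaves no hole in that endpoint.
- *The 10% share is an expected figure.* It equals the plan's whole drop-out allowance (Table 19 footnote). Phone-only loss should be smaller.

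**Conclusion.** The point holds in a limited form. As written, SAP 5.2.1.2 and 11.2.5 let any single contact make a dosed subject evaluable for the full 30-day window, and silence then counts as no event. The direction is known: under-reporting of a primary safety endpoint, most clearly in the tables after each vaccination.

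The size is modest: about 0.4 to 2 points at a true rate of 30% if 2% to 10% of dosed subjects are phone-only, and less after any vaccination. This rests on the assumed rate, the assumed shares and a constant hazard. At 10% the shift is small beside the half-width of the interval, which is (40.0 − 21.2)/2 = 9.4 points. It is still worth correcting, because the change is cheap and would match the SAP's own per-dose rule for solicited AEs.

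**What to change.** 1. In SAP 5.2.1.2 and the N table of 11.2.5, define 30-day evaluability dose by dose: the diary card for that dose was returned, or the 30-day visit (or a later safety contact covering the full 30 days) was completed. State that a call on Day 8-10 alone does not qualify.
2. Apply the rule whether or not an AE was reported. Admitting a phone-only dose only when an AE was reported makes inclusion depend on the outcome. With 90 followed subjects (27 events) and 10 phone-only subjects of whom about 1 reports, the rate would be 28/91 = 30.8% against a true 30%.
3. Use this denominator for the Unsolicited Safety Set tables. Keep the planned Exposed Set analysis as the all-vaccinated version, in which every reported AE is still counted and listed.
4. Align protocol 10.6 and the non-reporter sentence in SAP 11.2.5 with this.

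The phone question in protocol 8.1.3 need not be reworded for this purpose.

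Cost: SAP wording, an aligning change in protocol 10.6, and a per-dose flag from data already collected. Denominators become slightly smaller and AE rates slightly higher.
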